#### 1.1.4.4 CLINICAL STUDIES

A single and multiple dose ascending study of ATI-450 in healthy volunteers has been conducted: ATI-450-PKPD-101.

ATI-450-PKPD-101 consisted of multiple parts. A total of 32 male and female subjects were enrolled into Part A of the study where 4 ascending single doses (10 mg, 30 mg, 50 mg and 100 mg) were explored. Eight subjects were randomized at each dose level to receive a single oral dose of ATI-450 (n=6) or placebo (n=2). The 100 mg cohort was repeated following a high fat breakfast to explore the fed-fasting PK of ATI-450.

In Part B, 3 ascending multiple doses (10 mg twice daily [BID], 30 mg BID and 50 mg BID) were explored in 30 male and female subjects. Ten subjects were randomized to receive multiple oral doses (6.5 days) of ATI-450 (n=8) or placebo (n=2) at each dose level.

The potential for a PK drug-drug interaction between ATI-450 and methotrexate (MTX) was investigated in healthy male subjects after administration of a single 7.5 mg oral dose of MTX alone or after twice daily oral administration of ATI-450 at 50 mg (n=15).

Data demonstrate that ATI-450 was well tolerated at all doses in the study. No serious adverse events (SAEs) or severe intensity events were reported. The most common AEs (reported by 2 or more subjects who received ATI-450) were dizziness, headache, upper respiratory tract infection, constipation and abdominal pain. All events were

of mild intensity. A trend of a decrease in absolute neutrophil count (ANC) was observed concurrent with dosing of ATI-450 without correlated clinical sequelae. This effect is consistent with the pharmacodynamic profile of certain anti-TNF therapies. No subject had an ANC value <500 cells/ $\mu$ L. Other laboratory findings were generally unremarkable including CBC's, BMP, LFT, LDH and CPK. There were no findings of myocyte degeneration as noted in the pre-clinical rat model.

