##### 3.2.2 Secondary Endpoints

What is being measured	Measurement time frame	Measurement Tool
Change in 7 point-ordinal scale	Baseline, Day 3, Day 7, Day 14, Day 28 and follow-up.	Using WHO COVID-19 Ordinal scale measuring: Proportion and time to patients with greater than 2 point improvement on the 7 point categorical scale

Change in oxygen saturation-normalization	Baseline and continuous throughout hospitalization	Peripheral capillary pulse oximeter to measure: SpO 2 /FiO 2 ratio over time, sustainment of normalization in 24 hours, and relative shifts in SpO 2 /FiO 2 categories (<235, between 235 and 315, greater than 315) over time
Need for advanced respiratory care	Baseline and continuous throughout hospitalization	Derived from medical record: time of intubation in the ICU, duration of ICU care in days, duration of overall hospitalization in days
All-cause mortality	Baseline and through d60	Noted in patient medical record
Number and percent of adverse events (AEs) and serious adverse events (SAEs); mean change from baseline lab values, vital signs, and ECG	Baseline through day 14 or at discharge <d14, at d28 ±3, d45 ±3 and d60 ±3 (lab values will be examined up to d45) 	CTCAE v5.0; changes in CBC, CMP, Mg, PT/INR, PTT, GGT, hsCRP, D-dimer, LDH, ferritin, creatine kinase, troponin-i, procalcitonin; standard vital signs measurement with pulse ox; ECG
Proportion of participants with normalization of fever for 24h	Baseline through day 14 or at discharge <d14	Standard daily vital measurement and obtained from patient medical record
Development of new bacterial or fungal infection (AE of Special Interest)	Continuous throughout hospitalization	Noted in patient medical record
Incidence of ARDS  through day 14 or at discharge <d14	From day 1 though day 14 or at discharge <d14	Noted in patient medical record
Change in plasma cytokines IL-1β, IL-6, IL-8 and TNF-α	Baseline, day 3, day 7 (or discharge <d7), day 14 (or discharge >d7 and <d14)	Plasma collected from blood and assayed on Luminex panel performed by KUMC BBV Core

 For clarification, lab values will be collected at baseline, day 3, day 7 (or discharge <d7), day 14 (or discharge >d7 and <d14), at day 28 ±3, day 45 ±3. Vital signs, pulse ox will be collected baseline through day 14 or at discharge <d14, at d28 ±3, d45 ±3 and d60 ±3 (lab values will be examined up to d45)

 ARDS Criteria:

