#### **Safety Summaries**

The FAS population will be used for the analysis of safety data (AEs, exposure to study medication, clinical laboratory values, vital signs, and ECG).

AEs will be coded with the Medical Dictionary for Regulatory Activities. Treatment-emergent adverse events (TEAEs) are defined as AEs with an onset date on or after the date of first administration of study medication and before the date of last administration of study medication + 30 days. TEAEs will be presented by system organ class and preferred term in frequency tables. Patients with multiple AEs will be counted only once within each preferred term and system organ class. Key patient information for patients with an AE with an outcome of death, patients with SAEs, and patients with an AE leading to discontinuation of study medication will be listed.

Laboratory data (hematology, serum chemistry, coagulation, and urinalysis) will be converted to Système International units for reporting and processing purposes. Absolute values and changes from baseline will be presented descriptively. Laboratory data outside study specific reference ranges will be listed. Vital signs and ECG parameters will be presented descriptively.

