#### **16.2 Reporting Procedures**

##### **16.2.1 ADVERSE EVENT REPORTING**

Information for adverse events, whether reported by the participant, directly observed, or detected by physical examination, laboratory test or other means, will be collected, recorded, followed and reported in the study Case Report Form (CRF) as described in the following sections.

ALL adverse events experienced by participants will be monitored/collected/reported as follows:

- Adverse events will be monitored/collected/reported from the start of study treatment, throughout the study, and up to and including day 30 after the last dose of study drug or until the 30 day safety follow up.
- Adverse Events of Special Interest (AESI): Development of new bacterial or fungal infection in this study is an AESI, and should be reported regardless of severity or seriousness. Reporting should

be completed using the protocol specific AESI Reporting Form and FDA 3500 A MedWatch form and all supporting documents to both KUCC Regulatory department: [[contact]](mailto:[contact]) and [[contact]](mailto:[contact]) (or by fax to [contact]). AESI should also be entered in CRIS (Velos) system

- SERIOUS adverse events that meet the definition(s) of a serious adverse event will be monitored/collected/reported from start of study treatment, throughout the study, and up to and including day 30 after the last dose of study drug or until the 30 day safety follow up.

Participants who experience an ongoing adverse event related to a study procedure and/or study medication beyond 30 days will continue to be contacted by a member of the study team until the event is resolved, stabilized, or determined to be irreversible by the Sponsor-investigator.

Study participants should also be instructed to report any new serious post-study event(s) that might reasonably be related to participation in this study.

Medical conditions/diseases present before starting study treatment are considered adverse events only if they worsen after initiation of study drug.

Abnormal laboratory values or test results constitute adverse events only if they induce clinical signs or symptoms or require therapy. In this case they will be recorded on the Adverse Events CRF, along with the associated signs, symptoms or diagnosis.

All SAEs recorded throughout this study will be continued to be monitored until resolution or stabilization.

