The primary objective is to assess the efficacy of ATI-450 on hypoxic respiratory failure-free survival in patients with moderate-severe COVID-19 pneumonia at day 14.

Secondary Objectives:

- To assess the clinical efficacy of ATI-450 on respiratory function and survival in patients with moderate-severe COVID-19 pneumonia.
- To assess the safety of ATI-450 in patients with moderate-severe COVID-19 pneumonia.

Exploratory Objectives:

- To Assess the pharmacodynamics of ATI-450 in patients with moderate-severe COVID-19 pneumonia.

Outcome Measures

Primary Efficacy Measure

- Primary treatment responder: defined as any patient who is alive, free of respiratory failure (does not require supplemental oxygen (greater than pre-existing use)) and does not experience a negative intercurrent event on Day 14 of the trial.

An intercurrent event is one that occurs after the first dose of study medication and either precludes the observation of the primary variable/endpoint or affects its interpretation. The following is a list of negative intercurrent events that could occur during this study:

- Death
- Withdrawal from study
- Intubation and ventilation
- Rescue with a non-protocol specified treatment for cytokine release syndrome

The following is a list of positive intercurrent events that could occur during this study:

- Early hospital discharge due to recovery

A patient will be considered a treatment responder if the primary endpoint is missing following a positive intercurrent event. A patient will be considered a treatment non-responder for all observations (missing or not missing) following a negative intercurrent event.

Secondary Efficacy Measures

- Change from baseline in the WHO COVID-19 7-point ordinal scale over time (**BASELINE, DAY 7, DAY 14, DAY 28**).
- All-cause mortality through Day 60 (**DAY 7, DAY 14, DAY 28 AND FOLLOW-UP**.).
- Responder based on 7-point ordinal scale: Greater than 2-point improvement from baseline on the 7-point ordinal scale. (**BASELINE, DAY 7, DAY 14, DAY 28 AND FOLLOW-UP**.).
- Time to discharge from the hospital.

Safety assessments include:

- Adverse events

Exploratory measures include:

- Change in serum cytokine Interleukin (IL)-6 over time (baseline, d7, EOT, d28).
- Change in serum cytokine IL-8 over time (baseline, d7, EOT, d28).
- Change in serum cytokines IL-1 β over time (baseline, d7, EOT, d28).
- Change in serum cytokine Tumor Necrosis Factor (TNF- α) over time.

*EOT: end of treatment

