Descriptive statistics (number of observations, mean (standard deviation) or median (minimum, maximum)) will be provided for continuous variables, and counts and percentages will be presented for categorical variables for each group.

Primary Efficacy Analysis

The study is hypothesis generating. The primary assessment of efficacy for this study will be the point estimate and corresponding exact 90% confidence interval for the proportions of responders for the ATI-450 and Placebo groups. All subjects who are alive, free of respiratory failure (do not require supplemental oxygen) by Day 14 of the trial will be considered responders. The point estimate and corresponding 90% confidence interval will be derived based on sample proportions and the Copper-Pearson CIs for proportions for the two groups (categorical data analysis by Alan Agresti, 3rd edition).

Secondary Efficacy Analyses

Binary variables will be analyzed using the method like that described for the primary endpoint. In addition to the point estimate and confidence interval for the difference in proportions for binary endpoints, odds ratios, corresponding confidence intervals will be provided. For binary measures that are recorded over time, separate analyses will be conducted at each timepoint.

Continuous secondary efficacy endpoints will be analyzed by estimating group means and mean difference and 95% CIs at each time point. Missing data will be imputed with the single imputation methods described above (LOCF or WOCF).

For time to discharge from hospital, estimates of the median (50th percentile) will be provided for each treatment group and Kaplan-Meier Curves will be provided. A two-sided stratified log-rank test will be applied. The stratification factor will be baseline age group (<60 versus ≥ 60).

Exploratory Outcomes Analyses

For all the Cytokines, changes over time (baseline, d7, EOT, d28) will be summarized by descriptive statistics and trajectory plots. Any time point after the end of treatment (EOT) will not be measured.

Safety Summaries

AEs will be summarized using table format based on DSMB requirements (attached).

Missing Data Imputation

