Missing data for binary secondary endpoints will be treated in a similar manner as the primary endpoint. For secondary endpoints of a continuous nature, the last observation prior to the intercurrent event will be carried forward (LOCF) for all positive intercurrent events and the worst observation prior to the intercurrent event will be carried forward (WOCF) for all negative intercurrent events.

Primary efficacy analysis will be done on the Full Analysis Set (FAS) and the per protocol population. Secondary efficacy analyses and safety analysis will be done on FAS only.

The statistical analyses and summaries will be conducted with the SAS® software package version 9.4 or higher.

Attachments:

- *IIT-2020-ATI-450-COVID-19 _DSMB_AdverseEventListingShell.xls*
- *IIT-2020-ATI-450-COVID-19 DSMB ReportTableShells_2020_1008.doc*

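### The SAP names only adverse-event tables for safety and does not carry over the protocol's laboratory, vital-sign and ECG summaries, so a silent neutrophil fall would be shown by no summary it names

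*SAP*

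**What the plan says.** The SAP keeps safety as a secondary objective. Under Outcome Measures, the list introduced by "Safety assessments include" has one entry, adverse events. The Safety Summaries section is one sentence: "AEs will be summarized using table format based on DSMB requirements (attached". Two attachments are listed at the end, an adverse-event listing shell and "IIT-2020-ATI-450-COVID-19 DSMB ReportTableShells_2020_1008.doc". A general sentence under Statistical Analysis Methods says that descriptive statistics "will be provided for continuous variables, and counts and percentages will be presented for categorical variables for each group", without naming variables.

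The protocol plans more:

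- Section 3.2.2 lists average change from baseline in laboratory tests, vital signs and ECG as part of a secondary endpoint. It gives a separate line to "Development of new bacterial or fungal infection (AE of Special Interest".
- Section 15.3, Safety Summaries, covers laboratory data, vital signs and ECG on the Full Analysis Set. For laboratory data it states: "Absolute values and changes from baseline will be presented descriptively". It also promises a listing of values outside the reference ranges.
- Section 15 leaves the details of the summaries to the SAP.

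Two further protocol statements matter. Section 1.1.4.4 reports from Phase 1: "A trend of a decrease in absolute neutrophil count (ANC) was observed concurrent with dosing of ATI-450 without correlated clinical sequelae". Section 16.2.1 states: "Abnormal laboratory values or test results constitute adverse events only if they induce clinical signs or symptoms or require therapy".

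**The concern.** Adverse-event tables can stand in for laboratory tables only if the laboratory effect of interest becomes an adverse event. Here the effect that Phase 1 points to is a fall in neutrophils without clinical consequence, and section 1.3.1 lists acute neutropenia among the immediate risks. Under section 16.2.1, a fall of that kind is not an adverse event.

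An analyst working from the SAP alone would meet its safety section in full and still produce no named output showing this effect by arm. The trial tests no hypothesis and has about 10 patients per arm, so descriptive tables are its whole safety output. A secondary endpoint named in the protocol could go unreported.

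**Working it through.** The plan states no figure on this point to reproduce. The check sets the two documents side by side and then traces where a neutrophil fall would be recorded.

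**1. Planned outputs compared**

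| Safety output | Protocol | SAP text |
|---|---|---|
| Adverse-event tables | 15.3 | Named |
| Laboratory values and change from baseline | 3.2.2, 15.3 | Not named |
| Out-of-range laboratory listing | 15.3 | Not named |
| Vital signs | 3.2.2, 15.3 | Not named |
| ECG | 3.2.2, 15.3 | Not named |
| New bacterial or fungal infection as its own count | 3.2.2 only | Not named |

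The last row differs from the others. Section 15.3 contains no infection summary, so the SAP did not drop one from there. Section 16.2.1 also requires every new infection to be reported as an event of special interest whatever its severity, so infections do reach the adverse-event data.

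**2. Where a neutrophil fall would be caught**

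Inputs (x10^3/µl):

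- ANC at entry at least 1.5 (protocol 5.1.6).
- Therapy stops if ANC is below 0.5 or, separately, if the white cell count is below 1 (protocol 11.4).

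Percent fall = 100 x (1 − limit / baseline). The second limit of 1.0 is used because neutrophils are part of the white cell count: while ANC is at least 1.0, the white-cell criterion cannot be met either.

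| Baseline ANC | Fall to 1.0 (neither count criterion can be met) | Fall to 0.5 (ANC criterion not yet passed) |
|---|---|---|
| 1.5 (entry floor) | 1 − 1.0/1.5 = 33.3% | 1 − 0.5/1.5 = 66.7% |
| 3 (assumed) | 66.7% | 83.3% |
| 5 (assumed) | 80.0% | 90.0% |
| 8 (assumed) | 87.5% | 93.8% |

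The documents give no baseline distribution, so the last three rows are assumptions that show the range. Between ANC 1.0 and 0.5 the white-cell criterion may stop therapy first, so the right-hand column is an upper limit. A fall within these limits that is asymptomatic and untreated is not an adverse event under section 16.2.1. The SAP names no other safety output in which it would be seen.

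**3. The protocol is not consistent on when a laboratory value is an adverse event**

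- Section 16.2.1 requires signs, symptoms or therapy.
- Section 16.2.2 has clinically significant findings entered, and explains that term as needing medical intervention.
- Appendix A, Adverse Event Definition, allows an abnormal laboratory finding as an adverse event with no symptom requirement.
- Appendix A, Adverse Event Monitoring, includes abnormalities that need intervention, and counts additional testing as intervention.

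Whether a given neutrophil fall reaches an adverse-event table therefore depends on which section a site follows.

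**The case against.** The strongest reply is that the SAP defines its safety tables by reference to attached shells. Those files are not among the documents available, and the second is not labelled as limited to adverse events. It may hold laboratory tables. This stands as a limit: what can be shown is that the SAP text does not name these summaries, not that they were abandoned. Against it, the sentence that cites the attachment speaks only of adverse events.

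A second reply is that protocol 15.3 still promises the summaries and the SAP does not withdraw them. That also stands, but section 15 hands the detail to the SAP. The SAP replaces other protocol analyses without comment: the 70% interval for the difference in responders becomes 90% intervals within each group. Silence cannot be read safely as retention. The general sentence on continuous variables does not settle it, because the SAP lists no laboratory, vital-sign or ECG variable to which it could apply.

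Three stronger readings are tempting, and the documents do not support them:

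- *A neutrophil fall would appear nowhere.* Protocol 15.3 still commits to summaries and a listing. ANC below 0.5 is a defined stopping event whose reason goes into the case report form (11.4). Toxicity of grade 3 or higher goes to the DSMB (9.1.3). Appendix A could also admit the finding as an adverse event.
- *Infections cannot be counted by arm.* They are reportable adverse events, so they can be counted; only a dedicated table is missing.
- *A fixed number of neutrophil counts is lost.* Six study-day draws in 20 patients gives 6 x 20 = 120, but this is only nominal. The schedule also has a screening draw and daily standard-of-care values. Early discharge merges visits, Day 28 and Day 45 may become phone calls, and patients may die.

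**Conclusion.** The concern holds as a mismatch between protocol and SAP. The SAP text does not carry over the secondary endpoint of change in laboratory values, vital signs and ECG, or the summaries and listing in protocol 15.3. Under section 16.2.1, an asymptomatic, untreated neutrophil fall that meets no stopping criterion is shown by no summary the SAP names. For a patient at the entry floor, that leaves a fall of 33.3% outside both blood-count criteria with certainty, and up to 66.7% if the white-cell criterion is not met first.

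This rests on two assumptions: that the attached shells do not already contain these tables, and that sites apply section 16.2.1 rather than the wider wording in Appendix A. If either fails, the gap narrows. The consequence is incomplete safety reporting in a trial whose safety output is entirely descriptive; the primary efficacy result is not affected.

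**What to change.** In the SAP, under Outcome Measures and Safety Summaries:

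1. Restore, by arm and visit, descriptive values and changes from baseline for laboratory tests (including ANC and white cell count), vital signs and ECG.
2. Restore the listing of out-of-range laboratory values from protocol 15.3.
3. Add a count by arm of patients with a new bacterial or fungal infection, the event of special interest in protocol 3.2.2.
4. If an attached shell already holds any of these, cite it by name and table instead.

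Separately, reconcile protocol 16.2.1, 16.2.2 and the two Appendix A sections on when a laboratory abnormality counts as an adverse event, and say in the SAP which definition the tables use.

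The cost is a few descriptive tables and a short text change. The data are already collected under the protocol's schedule, with no new visits, samples or patients. If the shells already contain the tables, the cost is one reference.

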Sample Size Justification

Data from 20 patients (10 randomized to ATI-450 and 10 to Placebo) provide some preliminary information about the efficacy and safety of ATI-450. No hypothesis will be formally tested. The mean and exact 90% confidence intervals for within-group event rates will be estimated and no between group difference will be estimated.

Randomization and Blinding

Prior to the start of the study, the University of Kansas Medical Center will generate a list of randomization numbers that shall be transmitted to the assigned clinical packaging organization for study medication labeling. The randomization list will be stored with access limited to designated personnel for study medication labeling. The randomization list will be made available, as appropriate, to unblind the database.

In the treatment period, subjects will be assigned to 1 of the 2 treatment groups in a random manner and at a 1:1 ratio stratified by baseline age group (<60 versus \geq 60). At the Day 1 visit an investigational center staff member will assign study medication to eligible subjects by selecting an appropriate Subject Kit. The staff member must select Subject Kits in chronological sequence and in an ascending numerical order starting with the lowest available Subject Kit number. No Subject Kit number may be omitted or reused. The Subject Kit number is the randomization number.

This study uses a double-blind design. The study medications are indistinguishable in appearance, as packaged and labeled.

Analysis populations

- The Full Analysis Set (FAS) will include all patients who have been administered at least one dose of study medication. The FAS will be population used in the primary efficacy analysis. The FAS will also be the population used secondary efficacy analyses and summaries as well as the population used in all safety summaries. The FAS will be analyzed/summarized as randomized when applied to efficacy endpoints. The FAS will be analyzed/summarized as treated when applied to safety endpoints.
- The Per-Protocol population will include all FAS patients who have completed their Day 14 visit and have continued study drug administration through Day 14 or were successfully discharged prior to Day 14. The Per-protocol population will be used for the primary efficacy analysis. Summaries and analyses using the per-protocol population will be done as treated.

Statistical Analysis Methods

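### For a WHO-scale score missing after early discharge, the SAP's carry-forward rule and its responder rule contradict each other, and a death with no recorded score is entered below the death category

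*SAP*

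**What the plan says.** **Two endpoints share one scale.** The SAP's Secondary Efficacy Measures list "Change from baseline in the WHO COVID-19 7-point ordinal scale over time" and, separately, "Responder based on 7-point ordinal scale: Greater than 2-point improvement from baseline on the 7-point ordinal scale".

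**Analysis.** The SAP's Secondary Efficacy Analyses state: "Continuous secondary efficacy endpoints will be analyzed by estimating group means and mean difference and 95% CIs at each time point". The next sentence reads "Missing data will be imputed with the single imputation methods described above (LOCF or WOCF". The Sample Size Justification, by contrast, says that "no between group difference will be estimated".

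**Continuous rule (SAP, Missing Data Imputation; the same in Protocol 15.5).** After a positive intercurrent event the last earlier observation is carried forward. For the other kind, "the worst observation prior to the intercurrent event will be carried forward (WOCF) for all negative intercurrent events". The only positive event listed is early discharge due to recovery. The negative events are death, withdrawal, intubation and ventilation, and rescue treatment.

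**Binary rule (same SAP section).** Missing binary secondary data follow the primary endpoint, whose rule is: "A patient will be considered a treatment responder if the primary endpoint is missing following a positive intercurrent event".

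**The scale (Protocol Appendix B).** It runs from 0 to 8: 0 uninfected, 1 and 2 ambulatory, 3 to 7 hospitalised, 8 dead. Both documents nevertheless call it a 7-point scale.

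**The concern.** The ordinal change and the ordinal responder should be two summaries of the same score. Under these rules a missing score after discharge is given one value for the change and a different, incompatible status for the responder. A missing score after death is given a value that belongs to a living patient.

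Where scores are missing, the responder rate would then reflect an imputation convention and not the patient's state. The mean change would understate both recovery after discharge and death. With 10 patients per arm, a few such patients are enough to change how a result reads.

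**Working it through.** **Which rule applies to the change.** The SAP never labels the ordinal change continuous. Protocol 3.2.2 calls the scale categorical, and the SAP also says that "counts and percentages will be presented for categorical variables for each group". Continuous is still the likely reading, because no other SAP secondary measure could use LOCF or WOCF: mortality and the responder are binary, discharge is time-to-event, and the cytokines are exploratory.

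**Feasible baselines.** Patients are hospitalised (Protocol 5.1.4), so the score is at least 3. Room-air patients can qualify (5.1.5), so 3 is possible. Intubated patients are excluded (5.2.10), so it is at most 5.

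**Early discharge.** Improvement = baseline - score, and a responder needs more than 2. Read literally, the last score before discharge is an in-hospital score, so 3 is the best that can be carried.

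| Baseline | Carried 3 | Home = 2 | Home = 1 | Score 0 | Binary rule if missing |
|---|---|---|---|---|---|
| 3 | 0, no | 1, no | 2, no | 3, yes | responder |
| 4 | 1, no | 2, no | 3, yes | 4, yes | responder |
| 5 | 2, no | 3, yes | 4, yes | 5, yes | responder |

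The second and last columns conflict at every feasible baseline. However the change is classified, the binary rule also conflicts with Appendix B: a baseline-3 patient at home at 1 or 2, or a baseline-4 patient at 2, does not meet the criterion.

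**Death.** Any score before death is at most 7, or at most 5 without earlier intubation. A baseline-4 patient who dies with no score recorded after baseline is entered as a change of 0, where scoring death gives 8 - 4 = +4. The error per unscored death is 8 - 7 = 1 to 8 - 3 = 5 points, or 0.1 to 0.5 on a 10-patient arm mean.

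**Where scores can be missing.**
- Discharge on Days 8 to 13: Protocol 10.1.1, the 10.4 table and its footnote 16 make the discharge assessment the Day 14 visit, with the scale. A score is missing only if it was not taken.
- Discharge before Day 7: 10.1.1 makes it the Day 7 visit, while footnote 16 sends it to the Day 14 schedule. One of the two visits may be left empty.
- Day 28: the scale is scheduled, but Protocol 10.2.1 allows a phone contact without saying whether it is scored. The call after early discharge collects vital status, oxygen need and adverse events.
- After Day 28: no scale is scheduled (10.1.2, 10.4), yet the SAP lists the responder at follow-up.

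**Size, responder (assumed counts).** Take 10 patients, 8 discharged home early with the visit score missing (baseline 3: 1 patient; 4: 5; 5: 2), and 2 non-responders. Exact 90% intervals:
- binary rule: 8/10 (49.3 to 96.3%)
- home scored 1: 5 + 2 = 7/10 (39.3 to 91.3%)
- home scored 2: 2/10 (3.7 to 50.7%)

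**Size, mean change (assumed counts).** Baseline is 5 for all, and mean change = sum of scores / 10 - 5. Dead/intubated/oxygen/home is 3/1/2/4 on placebo and 1/1/1/7 on ATI-450.
- Scores 8, 6, 4, 2: 46/10 - 5 = -0.4 and 32/10 - 5 = -1.8; difference -1.4.
- Death and intubation recorded, discharge carried at 3: 50/10 - 5 = 0.0 and 39/10 - 5 = -1.1; difference -1.1.
- The same, carried at 4: 54/10 - 5 = +0.4 and 46/10 - 5 = -0.4; difference -0.8.

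A harm example, 1/1/4/4 against 4/0/2/4, gives +1.0 when outcomes are scored (-1.2 and -0.2). It stays at +1.0 with discharge carried at 3 and death recorded as 8 (-0.8 and +0.2).

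**The case against.** The strongest case against is one of reach. The protocol schedules the scale at discharge and at Day 28. If those scores are recorded and used, nothing is imputed and both endpoints rest on one score. Vital status is collected to Day 60, so a death without a recorded 8 should be uncommon. That stands, and it limits the point to scores that are truly missing.

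Four stronger readings are tempting, and the documents do not support them.

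- *Every early discharge is affected.* For discharges on Days 8 to 13 the discharge assessment is the Day 14 visit.
- *A discharged patient can never show more than 2 points.* The documents do not say whether the discharge-day score is in-hospital or ambulatory. If it is scored 1 or 2 and carried forward, the bound does not apply.
- *The mean difference collapses from -1.4 to -0.5 or -0.2.* With discharge carried at 3 or 4, those figures need deaths to be entered at 5. On recorded data that means overwriting observed scores, whereas the SAP's wording is about missing data and its word *all* refers to events, not observations. The same figures would arise without overwriting only if no death in either arm had a recorded 8 or any earlier worsening: (15 + 6 + 8 + 12)/10 - 5 = -0.9 and (5 + 6 + 4 + 21)/10 - 5 = -1.4 give -0.5.
- *The responder rate could be 8/10 or 0/10.* The first needs all eight scores missing; the second needs all eight discharge-day scores kept at 3 or more. These are different data states.

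It is also fair to say that assigning a home score is itself a convention, since a baseline-4 patient's status turns on 1 or 2. Hence both should be shown.

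**Conclusion.** The point holds for missing scores. After early discharge due to recovery, the SAP's two rules put the same patient at no more than 2 points of improvement and at more than 2. The first half assumes that the change is treated as continuous and the carried score is an in-hospital one. The conflict of the binary rule with Appendix B needs neither assumption. On the continuous reading, a death with no score is entered at 7 or less against a defined 8. These are stated rules that yield wrong values, so more than detail is lacking.

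The size is modest and rests on assumed counts: 10 percentage points of responder rate per affected patient in a 10-patient arm, and a mean difference of -1.4 moving to between -1.1 and -0.8 when only missing values are imputed and death is recorded as 8. A reader might infer that the main results are at risk. They are not: these are supportive endpoints in a 20-patient hypothesis-generating study, and the SAP's primary endpoint, mortality and safety summaries are unaffected. It should be fixed because the correction is simple.

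**What to change.** In the SAP:

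1. State that death is scored 8 at all later visits, that observed scores are always used, and that imputation fills only missing values.
2. State whether the discharge assessment is scored as in-hospital or ambulatory, and which visit it fills when discharge is before Day 7, reconciling the Day 7 heading in Protocol 10.1.1 with footnote 16 of 10.4.
3. Derive the ordinal change and the ordinal responder from that one set of scores, in place of the imported rule that a value missing after discharge is a response.
4. For patients known to be discharged home with no score, use an ambulatory score and show the responder result under both 1 and 2.
5. Reconcile the 7-point label with the 0 to 8 scale in Appendix B, and drop follow-up from the responder's visits.

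Protocol 15.5 carries the same imputation sentences and should be aligned.

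The cost is wording only, but the ordinal responder rate may look less favourable: in the example it falls from 8/10 to 7/10 or 2/10. For the means, scoring home as 1 instead of 2 moves the benefit example from -1.4 to -1.7 (42/10 - 5 = -0.8 and 25/10 - 5 = -2.5) and leaves the harm example at +1.0 (-1.6 and -0.6).
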